# Table 5 Criteria for Continuing Study Drug Following Second Repeat Cardiac Evaluation in Patients with LVEF below LLN and <20%	Relative Change from Baseline

Institution's Range	LVEF Relative Change From Baseline	Action to be Taken
below LLN	≥20%	permanently withdraw study drug repeat cardiac evaluation every 4 wks for at least 16 wks or until resolution
below LLN	<20%	permanently withdraw study drug repeat cardiac evaluation every 4 wks for at least 16 wks or until resolution
WNL	≥20%	permanently withdraw study drug repeat cardiac evaluation every 4 wks for at least 16 wks or until resolution
WNL	<20%	continue at reduced dose (1250mg OD) continue cardiac evaluation every 2 months; refer to Time & Events Table 8

Abbreviations: LLN = lower limit of normal; LVEF = left ventricular ejection fraction; WNL = within normal limits

# Table 6Criteria for Continuing Study Drug Following Second Repeat
Cardiac Evaluation in Patients with LVEF WNL and ≥20% Relative
Change from Baseline

Institution's Range	LVEF Relative Change From Baseline	Action to be Taken
below LLN	≥20%	permanently withdraw study drug repeat cardiac evaluation every 4 wks for at least 16 wks or until resolution
below LLN	<20%	permanently withdraw study drug repeat cardiac evaluation every 4 wks for at least 16 wks or until resolution
WNL	≥20%	Reduce to 5 tablets (equivalent to 1250mg OD active drug) continue cardiac evaluation every 2 months; refer to Time & Events Table 8.
WNL	<20%	continue study drug continue cardiac evaluation every 3 months; refer to Time & Events Table 8.

Abbreviations: LLN = lower limit of normal; LVEF = left ventricular ejection fraction; WNL = within normal limits

**NOTE:** If **following a dose reduction**, a subject experiences a  $\ge 20\%$  decrease in LVEF relative to baseline **OR** the LVEF is below the institution's LLN, the subject will be permanently withdrawn from study drug and cardiac evaluations must be performed every 4 weeks for at least 16 weeks or until resolution.

 $A \ge 20\%$  relative decrease from baseline in LVEF (asymptomatic or symptomatic), that is below the institution's LLN is considered an SAE and must be reported to GSK (refer to Section 9 for definition of an SAE).

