## 7.3.1. Criteria for Evaluating Asymptomatic Cardiac events

If a subject who is receiving full dose of Lapatinib experiences a  $\geq 20\%$  decrease in LVEF relative to baseline AND the LVEF is below the institution's lower limit of normal (LLN), another evaluation of LVEF must be performed 2 weeks later while still receiving study drug.

Upon completion of the first repeat evaluation of LVEF, the procedures described in Table 3, Table 4, Table 5, and Table 6 must be followed:

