# Table 3Criteria for Continuing Study Drug Following First Repeat Cardiac
Evaluation Performed 2 Weeks Later While Still Receiving Study
Drug

Institution's Range	LVEF Relative Change From Baseline	Action to be Taken
below LLN	≥20%	temporarily withdraw study drug repeat cardiac evaluation in 2 wks and follow procedures in Table 4
below LLN	<20%	reduce to 5 tablets (equivalent to 1250mg QD active drug) repeat cardiac evaluation in 2 wks & follow procedures in Table 5
WNL	≥20%	continue study drug repeat cardiac evaluation in 2 wks and follow procedures in Table 6
WNL	<20%	continue study drug continue cardiac evaluation every 2 months; refer to Time & Events Table 8.

Abbreviations: LLN = lower limit of normal; LVEF = left ventricular ejection fraction; WNL = within normal limits

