# Table 4Criteria for Continuing Study Drug Following Second Repeat
Cardiac Evaluation in Patients with LVEF below LLN and ≥20%
Relative Change from Baseline

Institution's Range	LVEF Relative Change From Baseline	Action to be Taken
below LLN	≥20%	permanently withdraw study drug repeat cardiac evaluation every 4 wks for at least 16 wks or until resolution
below LLN	<20%	permanently withdraw study drug repeat cardiac evaluation every 4 wks for at least 16 wks or until resolution
WNL	≥20%	permanently withdraw study drug repeat cardiac evaluation every 4 wks for at least 16 wks or until resolution
WNL	<20%	reduce to 5 tablets (equivalent to 1250mg QD active drug) continue cardiac evaluation every 3 months; refer to Time & Events Table 8.

Abbreviations: LLN = lower limit of normal; LVEF = left ventricular ejection fraction; WNL = within normal limits

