## 8.4.5. Criteria for Evaluating Asymptomatic Cardiac events

Cardiac Events will be obtained for at Screening and on Day 1, every 2 Cycles (8 weeks) until discontinuation of study treatment or as clinically needed.

If a subject experiences a  $\geq 20\%$  decrease in LVEF relative to baseline AND the LVEF is below the institution's lower limit of normal (LLN), another evaluation of LVEF must be performed 2 weeks later while still receiving study drug.

Upon completion of the first repeat evaluation of LVEF, the procedures described in Section 7.3.1 must be followed.

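### After a dose reduction, Section 7.3.1 withdraws a subject whose LVEF falls, while Sections 8.4.5 and 9.2 keep her on drug for a repeat test

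*Protocol*

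**What the plan says.** Protocol Section 7.3.1 starts its repeat-on-drug rule with a dose condition: "If a subject who is receiving full dose of Lapatinib experiences a" relative LVEF decrease of 20% or more, together with a value below LLN, she is retested 2 weeks later on drug and then managed by Tables 3 to 6. The NOTE after Table 6 covers the period after a dose reduction. There, either criterion alone is enough, and "the subject will be permanently withdrawn from study drug and cardiac evaluations must be performed every 4 weeks". These evaluations run for a minimum of 16 weeks or end at resolution.

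Section 8.4.5 has the same title and the same two-part trigger but no dose condition. It requires that "another evaluation of LVEF must be performed 2 weeks later while still receiving study drug", and it refers to 7.3.1 only once that first repeat is done.

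Section 9.2, in its paragraph on treatment modification for cardiac dysfunction, also has no dose condition. It asks for:

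- a repeat 1-2 weeks later on lapatinib;
- a temporary stop if the fall is confirmed;
- if LVEF recovers within 3 weeks, a possible restart at a reduced dose after consultation with the sponsor;
- withdrawal if a repeat still shows both criteria.

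Sections 6.5, 7.3 and 9.2 withdraw Grade 3-4 left ventricular dysfunction at any dose. Section 7.3.1 adds that meeting both criteria "is considered an SAE and must be reported to GSK".

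**The concern.** The full-dose condition is what separates the repeat-on-drug route from the NOTE. Without it, 8.4.5 and 9.2 also apply to subjects for whom the NOTE orders permanent withdrawal. A site cannot stop the drug for good and also keep the subject on it until a repeat test. Whichever section it follows, it departs from another, and compliance cannot be judged. The rule concerns a cardiac risk that the protocol itself describes in Section 2.2, including symptomatic cases.

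**Working it through.** **Test case.** A subject on 1250 mg has an LVEF at least 20% below baseline and below LLN, without Grade 3-4 dysfunction.

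| Text | Trigger | Dose scope | Action at first detection |
|---|---|---|---|
| 7.3.1, opening rule | both criteria | full dose only | not applicable to her |
| 7.3.1, NOTE | either criterion | after a reduction | permanent withdrawal |
| 8.4.5 | both criteria | none stated | stay on drug, mandatory repeat at 2 weeks |
| 9.2 | both criteria | none stated | stay on drug, recommended repeat at 1-2 weeks, temporary stop if confirmed |

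The last two rows cannot be followed together with the NOTE.

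**How a subject comes to be on 1250 mg.**

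- Table 3, below LLN with a fall under 20%: "reduce to 5 tablets (equivalent to 1250mg QD active drug". Table 5 then lets her "continue at reduced dose (1250mg OD" if LVEF is back within normal limits with a fall under 20%.
- Table 6, within normal limits but a fall of 20% or more: "Reduce to 5 tablets (equivalent to 1250mg OD active drug".
- Table 4, after a hold, within normal limits with a fall under 20%: "reduce to 5 tablets (equivalent to 1250mg QD active drug) continue cardiac evaluation every 3 months".
- Table 2, for diarrhea, rash or other toxicity. This counts if the NOTE covers any reduction; its wording names no type.

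**Where there is no conflict, or less of one.**

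1. Grade 3-4 dysfunction leads to withdrawal at every dose.
2. A subject stopped and restarted at a reduced dose (Table 4, or 9.2's own path) who again meets both criteria is also withdrawn under the natural reading of 9.2. For her, only 8.4.5 conflicts with the NOTE. That 9.2 clause still needs both criteria where the NOTE needs one.

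**Extra exposure at 1250 mg/day after both criteria are met.**

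- NOTE: 0 doses.
- 8.4.5: about 14 doses, 14 × 1250 = 17,500 mg.
- 9.2: about 7-14 doses, 7 × 1250 = 8,750 mg to 17,500 mg.

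**Expected number of subjects** = N × rate of LVEF decrease × share on a reduced dose. The rates, 1.3% and 1.6%, are in the safety profile in Section 2.2. N is 62 (full enrolment) or 32 (2 × 16, first stage). The protocol gives no dose-reduction rate, so a share of 10-40%, independent of LVEF, is assumed.

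- 62 × 0.013 × 0.10 = 0.08; 62 × 0.016 × 0.40 = 0.40.
- 32 × 0.013 × 0.10 = 0.04; 32 × 0.016 × 0.40 = 0.20.

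These figures are likely too high. The reported rates count any LVEF decrease, not both criteria without Grade 3-4. Independence also fails for the cardiac routes, where LVEF caused the reduction and a second fall in the same subject is needed.

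**The case against.** The strongest reply is that 7.3.1 is plainly meant to lead. It is the dose-modification section, and its NOTE is the only text written for subjects already reduced. The protocol summary and Sections 5.1 and 6.5 point to 7.3, and 9.5 points to 7.3.1. Table 2 sets left ventricular dysfunction aside for separate treatment. Section 7.3.1 refers to Section 9 only for the SAE definition. Section 8.4.5 looks like a shortened copy of 7.3.1, not a second rule. This makes continued dosing less likely. It does not settle the matter: no precedence is stated, 8.4.5 sends the reader to 7.3.1 only after the on-drug repeat, and the 9.2 paragraph does not refer to 7.3.1 at all.

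It can also be said that the harm is small. The protocol accepts two more weeks on drug at 1500 mg for the same finding, and the milligram totals only restate the days of dosing. Meeting both criteria is an SAE reported within 24 hours under 9.7.3, so the sponsor may step in. A restart under 9.2 would need sponsor consultation and a second reduction, which Table 1 normally takes off study. All of this stands and limits the extra exposure mainly to the repeat interval. But the reporting rules give no dosing instruction, and a subject already reduced is the one for whom the NOTE is deliberately stricter.

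Section 9.2 differs from 7.3.1 in other ways, such as repeat timing, recovery window and later monitoring. Those are separate points.

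**Conclusion.** The concern holds as an internal inconsistency in the current text. For a reduced-dose subject who meets both LVEF criteria without Grade 3-4 dysfunction, the NOTE in 7.3.1 contradicts 8.4.5 in every case. It contradicts 9.2 unless she came through a stop and restart. The consequence is about 7-14 extra daily doses in an expected 0.08-0.40 of 62 subjects. That range rests on the assumed 10-40% reduced-dose share and on independence, and is best read as an upper-end illustration. No endpoint, sample size or error rate is affected. It should be corrected because it concerns a cardiac stopping rule and costs little to put right.

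**What to change.** 1. Add the full-dose condition of 7.3.1 to the repeat-on-drug sentences in 8.4.5 and 9.2.
2. State in both sections that, after a dose reduction, the NOTE in 7.3.1 applies from first detection of the fall.
3. Change 9.2's withdrawal clause after re-challenge so that either criterion is enough, as in the NOTE.

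Keep 9.2's Grade 3-4 withdrawal sentence and its LVEF checks at 2 and 4 weeks and then every 4 weeks after re-challenge. Replacing the treatment text in 8.4.5 and 9.2 with one reference to 7.3.1, including its NOTE, would also remove the conflict, provided those two elements of 9.2 are retained.

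The cost is wording in the next amendment and a letter to sites. No new assessments are needed.

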## 7.3.2. Liver Chemistry Stopping and Follow Up Criteria

## 7.3.2.1. Liver Chemistry Stopping Criteria

Liver chemistry stopping and follow up criteria have been designed to assure subject safety and evaluate liver event etiology. All subjects who meet liver chemistry criteria requiring permanent discontinuation of investigational product must continue to be followed for the study assessments and procedures as defined in Section 8. Study Assessments and Procedures and at the time points indicated in the Time & Events Table 8 in Section 8. Study Assessments and Procedures.

If a subject experiences ALT  $>3 \times$  ULN and total bilirubin  $>2.0 \times$  ULN (>35% direct; bilirubin fractionation required\*), then the following actions must be taken:

- immediately and permanently discontinue investigational product;
- complete the SAE data collection tool, the liver event CRF, and the liver imaging and/or liver biopsy CRFs, if these tests are performed;
- in addition to the liver event follow up assessments defined in Section 7.3.2.2 Liver Chemistry Follow-up Criteria below, the following are suggested: specialist or hepatology consultation; anti-nuclear antibody, anti-smooth muscle antibody, and Type 1 anti-liver kidney microsomal antibodies; and liver imaging and/or liver biopsy to evaluate liver disease;
- promptly report the event to GSK within 24 hours of learning its occurrence (refer to Section 9.7.3. Prompt Reporting of Serious Adverse Events and other Events to GSK for guidance on prompt reporting to GSK);
- monitor every week until liver chemistries resolve, stabilize or return to within baseline values;
- do not re-challenge with investigational product.

\***NOTE**: bilirubin fractionation should be performed if testing is available. If testing is unavailable and a subject meets the criterion of total bilirubin  $>2.0 \times ULN$ , then the aforementioned actions must still be performed.

If a subject experiences:

- ALT >8  $\times$  ULN or
- ALT >5 × ULN persisting for ≥2 weeks : retest within 3 days from the first occurrence and then weekly to determine if ALT elevation persists or
- ALT >3 × ULN with signs or symptoms of hepatitis or hypersensitivity (the appearance or worsening of fatigue, nausea, vomiting, right upper quadrant pain or tenderness, fever, rash, or eosinophilia),

#### GM2007/00215/03

#### CONFIDENTIAL

then hold investigational product for 2 weeks, repeat liver chemistry testing in 2 weeks, and then call the Medical Monitor to discuss the possibility of re-challenging with investigational product.

If the treatment is exhibiting efficacy **and** the subject wants to continue for potential benefit of lapatinib therapy after being informed of the results of liver chemistry testing, then the investigational product may be re-started at the reduced dose agreed upon by the investigator and the Medical Monitor. The liver event CRF should be completed and liver chemistries and aforementioned signs and symptoms should be monitored at a minimum of every 2 weeks until resolution, stabilization, or a return to baseline values, at which point monitoring should be continued per protocol.

If a subject experiences ALT >3 × ULN **but** <5 × ULN **and** total bilirubin  $\leq$ 2 × ULN, without signs or symptoms of hepatitis or hypersensitivity, **and** who can be monitored weekly, then the following actions should be taken:

- continue investigational product;
- monitor weekly until liver chemistries resolve, stabilize, or return to within baseline, then monitor liver chemistries as per protocol assessment schedule;
  - if ALT >3 and  $< 5 \times$  ULN for > 4 weeks, discontinue the treatment;
- if at any time this subject meets any of the aforementioned liver chemistry stopping criteria, then proceed as described above.

### 7.3.2.2. Liver Chemistry Follow up Criteria

For all subjects who meet any of the liver chemistry criteria described above, make every attempt to carry out the liver event follow up assessments described below:

- Viral hepatitis serology including:
  - Hepatitis A IgM antibody;
  - Hepatitis B surface antigen and Hepatitis B Core Antibody (IgM);
  - Hepatitis C RNA;
  - Cytomegalovirus IgM antibody;
  - Epstein-Barr viral capsid antigen IgM antibody (or if unavailable, obtain heterophile antibody or monospot testing);
  - Hepatitis E IgM antibody (if subject resides or has travelled outside USA or Canada in past 3 months);
- Serum creatine phosphokinase (CPK) and lactate dehydrogenase (LDH);
- Complete blood count with differential to assess eosinophilia;
- Record the appearance or worsening of clinical symptoms of hepatitis, or hypersensitivity, fatigue, decreased appetite, nausea, vomiting, abdominal pain, jaundice, fever, or rash as relevant on the AE report form;

- Record use of concomitant medications, acetaminophen, herbal remedies, other over the counter medications, or putative hepatotoxins, on the concomitant medications report form;
- Record alcohol use on the liver event alcohol intake case report form.

Refer to Section 15.5, Appendix 5 for a liver safety algorithm detailing stopping and follow up criteria.

A blood sample for PK analysis (approx. 3ml- see Study Manual) should be obtained for measurement of lapatinib concentration as soon as possible after the event is reported. The date, time, and amount of the last dose ingested by the subject, and the date and time at which the blood sample is obtained, should be recorded. Please see the Study Manual for PK sample instructions and collection details.

# 7.4. Packaging and Labeling

The contents of the label will be in accordance with all applicable regulatory requirements.

# 7.5. Handling and Storage

Lapatinib will be dispatched to a site only after receipt of required documents in accordance with applicable regulatory requirements and GSK procedures.

Investigational product must be stored in a secure area under the appropriate physical conditions for the product. Access to and administration of the investigational product will be limited to the investigator and designee. Lapatinib must be kept at room temperature (15-30°C) and a temperature log must be filled.

Investigational product must be dispensed or administered only to subjects enrolled in the study and in accordance with the protocol.

A Material Safety Data Sheet (MSDS) describing the occupational hazards and recommended handling precautions will be provided to site staff if required by local laws or will otherwise be available from GSK upon request.

# 7.6. Treatment Assignment

All subjects will receive open-label Lapatinib with 1500 mg QD dosing.

# 7.7. Product Accountability

In accordance with local regulatory requirements, the investigator, designated site staff, or head of the medical institution (where applicable) must document the amount of GSK investigational product dispensed and/or administered to study subjects, the amount returned by study subjects, and the amount received from and returned to GSK, when

applicable. Product accountability records must be maintained throughout the course of the study.

# 7.8. Treatment Compliance

A record of the number of tablets dispensed to and taken by each subject at each visit must be maintained and reconciled with the study medication and compliance records in the CRF.

At each site visit, the cause of any missed doses should be discussed. Any AE(s) associated with missed doses must be recorded in the CRF. Subjects should be instructed for the importance of compliance to study treatments.

# 7.9. Concomitant Medications and Non-Drug Therapies

## 7.9.1. Permitted Medications and Non-Drug Therapies

All concomitant medications taken during the study will be recorded in the CRF. The minimum requirement is that drug name and dates of administration are to be recorded. In addition, indication and dose information should also be captured on the CRF, if possible. If there are any questions on medications not listed below, please contact the medical monitor of GSK for further information and clarification.

The following will be recorded on the appropriate CRF pages:

- A complete list of prescription and over-the-counter medications that have been taken within 4 weeks prior to the first dose of study drug.
- All concomitant medications taken while subjects are receiving study drug.

Subjects should receive full supportive care during the study, including transfusion of blood and blood products, and treatment with antibiotics, antiemetics, antidiarrheals, and analgesics, as appropriate. Refer to Section 9.5 for supportive care guidelines for diarrhea.

Concomitant treatments with bisphosphonates and/or radiotherapy are allowed for non target bone lesion(s) prior to enrollment.

# 7.9.2. Prohibited Medications and Non-Drug Therapies

Lapatinib is a substrate for CYP3A4. Inducers and inhibitors of CYP3A4 may alter the metabolism of Lapatinib. Co-administration of lapatinib with weak or moderate inhibitors or inducers of CYP3A4 must be at the discretion of the prescribing physician and based on a risk/benefit assessment. The list of CYP3A4 inducers and inhibitors are prohibited from screening through discontinuation from study. Additionally, there may be potential interaction between Lapatinib and warfarin. Patients have experienced elevated INRs and bleeding with warfarin and quinazolines. Patients on warfarin and Lapatinib should have more frequent INR/PT determinations after starting Lapatinib (e.g. weekly

for the first month and weekly for a minimum of 2 weeks following discontinuation of Lapatinib).

All Herbal (Alternative) medicines are prohibited as well as medications that modify gastric pH.

Concurrent surgery and radiotherapy on target lesion (unless initiated as adjuvant therapy for treatment of the initial diagnosis of invasive breast cancer) is prohibited during the study treatment.

The list of prohibited medications from screening through discontinuation from study is in Table 7.

Drug Class	Agent	Wash-out 		
CYP3A4 Inducers				
Antibiotics	all rifamycin class agents (e.g., rifampicin, rifabutin, rifapentine)	14 days		
Anticonvulsants	phenytoin, carbamazepine, barbiturates (e.g., phenobarbital)			
Antiretroviral	efavirenz, nevirapine			
Glucocorticoids (oral)	cortisone (>50 mg), hydrocortisone (>40 mg), prednisone (>10 mg), methylprednisolone (>8 mg), dexamethasone (>1.5 mg) 			
Other	St. John's Wort, modafinil			
CYP3A4 Inhibitors				
Antibiotics	7 days			
Antifungal	biotics clarithromycin, erythromycin, troleandomycin fungal itraconazole, ketoconazole, fluconazole (>150 mg daily), voriconazole			
Antiretroviral, Protease Inhibitors	delaviridine, nelfinavir, amprenavir, ritonavir, indinavir, saquinavir, lopinivir	-		
Calcium channel blockers				
Antidepressants	nefazodone, fluvoxamine	-		
GI Agents	cimetidine, aprepitant			
Other	grapefruit, grapefruit juice	-		
	amiodarone	6 months		
Miscellaneous	1	1		
Antacids	Mylanta, Maalox, Tums, Rennies 1 hour before and dosing			
Herbal supplements 	Ginkgo biloba, kava, grape seed, valerian, ginseng, echinacea, evening primrose oil.	14 days		

#### Table 7 Prohibited Medications

1. At the time of screening, if a patient is receiving any of the above listed medications/substances, the medication or substance must be discontinued (if clinically appropriate) for the period of time specified prior to administration of the first dose of study drug and throughout the study period in order for the patient to be eligible to participate in the study.

2. Glucocorticoid daily doses (oral) ≤ 1.5 mg dexamethasone (or equivalent) are allowed. Glucocorticoid conversions are provided in parentheses.

3. This list is not all-inclusive; therefore, for herbal supplements not listed, please contact the GSK Medical Monitor or Clinical Scientist.

NOTE: if future changes are made to the list of prohibited medications, a formal documentation will be created and stored with the study file. Any changes will be communicated to the investigative sites in the form of a letter.

